3.8 Summary of Known and Potential Risks and Benefits

No prior clinical studies with SB623 have been conducted. Based on the available animal data, no risks have been identified, but considerable potential benefit in reversing neurological deficits has been observed in a rat model of stroke.

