9.0 INVESTIGATIONAL PLAN

9.1 Overall Study Design

This is an open-label study of stereotactic, intracranial injection of SB623 cells (SB623 cells) in patients with hemiparesis from stable ischemic stroke who have remained stable during the

prior 3 weeks (as documented by NIHSS assessments at weeks -3 and -1). Three cohorts will receive escalating singe doses of SB623, which are to be stereotactically implanted into grey or white matter sites adjacent to the infarct region. One burr-hole craniostomy will be created, and cells implanted using 3 needle tracks with 5 cell deposits for each track at varying depths. Cell implantation will be standardized as to volume (20 uL/deposit) and rate $(10 \,\mu L/min)$, with spacing between each implant of approximately 5-6 mm. Each deposit is expected to take approximately 2-3 minutes, with each needle track being completed within 15 minutes. Each cohort will consist of 6 subjects defined by an increasing total number of cells implanted. Safety will be monitored by the Investigator, Principal Monitor, Medical Monitor, and an external Data Safety Monitoring Board (DSMB). For the first cohort, a single patient will first be dosed, then evaluated over a 2 week period for safety prior to dosing the next member of this cohort. This 2-week interval will continue between each of the remaining members of the cohort. If the safety profile is acceptable for a cohort, and after review by the DSMB, the first patient in each subsequent, sequential cohort will be dosed, beginning 4 weeks after dosing of the last patient of the prior cohort. For the second and third patients in each of the subsequent cohorts, there will be an interval of 2 weeks after the prior patients prior to further enrollment.

Safety will be monitored by clinical symptoms, laboratory findings, and MRI brain imaging. Efficacy will be determined based on changes in the clinical measures of stroke and on FDG-PET brain imaging.

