A dose-limiting toxicity will be defined as any grade 3 or 4 events which are at least possibly related to study product or administration procedure. If the first patient in a cohort has a dose-limiting toxicity attributable to the SB623 cells, then no further patients will be dosed in that cohort until a comprehensive evaluation has been conducted. If 2 of 6 patients in a cohort have a dose-limiting toxicity attributable to the SB623 cells, then no further patients will be dosed in that or other higher-dose cohorts. Each dose-limiting-toxicity will be evaluated by the DSMB. The DSMB shall be the final arbitrator for attributions.

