14.0 STOPPING RULES

A dose-limiting toxicity will be defined as any grade 3 or 4 events which are at least possibly related to study product or administration procedure. If the first patient in a cohort has a dose-limiting toxicity attributable to the SB623 cells, then no further patients will be dosed in that cohort until a comprehensive evaluation has been conducted. If 2 of 6 patients in a cohort have a dose-limiting toxicity attributable to the SB623 cells, then no further patients will be dosed in that or higher-dose cohorts. Each dose-limiting-toxicity will be evaluated by the DSMB.

In addition, adverse events attributable to the surgical procedure, such as intracranial infection, intracranial bleeding, or seizures, shall be subject to review by the DSMB

The DSMB shall be the final arbitrator for attributions.

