17.0 EXTERNAL DATA SAFETY MONITORING BOARD

An External Data Safety Monitoring Board (DSMB) will continuously evaluate toxicity and mortality rates, and recommend appropriate actions, according to the DSMB Charter.

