18.5 Determination of Sample Size

The sample size of 6 patients per cohort was determined based on safety considerations. Based on the animal safety studies, no dose-limiting toxicity is anticipated. However, if the true rate is 40%, a sample size of 6 patients per cohort would result in a < 5% chance of missing a dose-limiting toxicity.

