3. STUDY DESIGN

3.1 OVERVIEW

This is an open-label safety study of stereotactic, intracranial injection of SB623 cells in patients with hemiparesis from stable ischemic stroke who have remained stable during the prior 3 weeks (based on NIHSS assessments at weeks -3 and -1). While primarily a safety study, efficacy parameters will also be evaluated. Three cohorts will receive escalating singe doses of SB623, which are to be stereotactically implanted into grey or white matter sites adjacent to the infarct region. One burr-hole craniostomy will be created, and cells implanted using 3 needle tracks with 5 cell deposits for each track at varying depths around the damaged area. Cell implantation will be standardized as to volume (20 μ L/deposit) and rate (10 μ L/min), with spacing between each implant of approximately 5-6 mm. Each deposit is expected to take approximately 2-3 minutes, with each needle track being completed within 15 minutes. Each cohort will consist of 6 patients defined by an increasing total number of cells implanted. Safety will be monitored by the Investigator, Principal Monitor, Medical Monitor, and an external Data Safety Monitoring Board (DSMB). For the first cohort, a single patient will first be dosed, then evaluated over a 2 week period for safety prior to dosing the next member of the cohort. This 2-week interval will continue between each of the remaining members of the cohort. If the safety profile is acceptable for a cohort, and after review by the DSMB, the first patient in each subsequent cohort will be dosed, beginning 4 weeks after dosing of the last patient of the prior cohort. For the second and third patients in each of the subsequent cohorts, there will be an interval of 2 weeks after the prior patients prior to further enrollment.

SanBio Incorporated Protocol SB-STR01

A dose-limiting toxicity (DLT) will be defined as any grade 3 or 4 events which are at least possibly related to study product or administration procedure. If the first patient in a cohort has a DLT attributable to the SB623 cells, then no further patients will be dosed in that cohort until a comprehensive evaluation has been conducted. If 2 of 6 patients in a cohort have a DLT attributable to the SB623 cells, then no further patients will be dosed in that or other higher-dose cohorts. Each DLT will be evaluated by the DSMB. The DSMB shall be the final arbitrator for attributions.

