7.6 DATA SAFETY AND MONITORING BOARD

The members of the Data Safety and Monitoring Board (DSMB) will be experts who are independent from the sponsor, formed to continuously evaluate toxicity and mortality rates. The procedures and responsibilities for the collection, analysis, and review of the data by the DSMB as well as communication and documentation of their opinions and recommendations are defined in the DSMB charter.

The DSMB will review the safety profile of all patients in each cohort. If the safety profile is deemed acceptable by the DSMB for a given cohort, the first patient in each subsequent cohort will be dosed, beginning 4 weeks after dosing of the last patient of the prior cohort. Two or more serious adverse events will trigger a review by the DSMB before continuing enrollment. Each DLT will be evaluated by the DSMB. The DSMB shall be the final arbitrator for attributions.

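### A single SB623-attributable DLT holds dosing only if it is in a cohort's first patient; after a later one, the supplied documents do not make dosing wait for the DSMB's evaluation

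*Protocol*

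**What the plan says.** Protocol 9.1, Protocol 14.0, the Protocol synopsis and SAP 3.1 define a DLT as a grade 3 or 4 event at least possibly related to product or procedure. They then give the same two dosing rules, both limited to DLTs attributable to the cells:

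- **Single DLT.** Protocol 9.1: "If the first patient in a cohort has a dose-limiting toxicity attributable to the SB623 cells, then no further patients will be dosed". The pause applies to the cohort concerned and ends once the event has been fully evaluated. SAP 3.1 matches: "If the first patient in a cohort has a DLT attributable to the SB623 cells, then no further patients will be dosed".
- **Two DLTs.** Two of six patients in a cohort stop that cohort and any higher dose.

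On DSMB review, Protocol 14.0 adds: "Each dose-limiting-toxicity will be evaluated by the DSMB". The DSMB has the last word on attribution. Protocol 17.0 says that it "will continuously evaluate toxicity and mortality rates, and recommend appropriate actions, according to the DSMB Charter". SAP 7.6 and the synopsis add: "Two or more serious adverse events will trigger a review by the DSMB before continuing enrollment".

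On pacing (Protocol 9.1), cohort 1 has 2 weeks between all patients. In cohorts 2 and 3 an interval is given for the second and third patients only: "there will be an interval of 2 weeks after the prior patients prior to further enrollment".

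**The concern.** The single-DLT hold depends on the patient's position in the cohort. If patient 1 has an attributable DLT, dosing stops until it is evaluated. If patient 2 or 3 has one, the DSMB must evaluate it, but nothing in the documents supplied suspends dosing meanwhile. The 2-of-6 stop counts attributable DLTs, so it may not act on an event whose attribution is still open.

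The first-patient limit applies in every cohort. In cohort 1 the 2-week gaps give some time for a ruling. In cohorts 2 and 3, at 5 and 10 million cells against 2.5 million in cohort 1, patients 4-6 could be implanted before a known DLT in patient 2 or 3 is ruled on. An implant cannot be withdrawn, and experience is thin: the Protocol (3.8) records that "No prior clinical studies with SB623 have been conducted", so each higher dose opens on what the earlier cohorts of this trial have shown.

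**Working it through.** **Inputs.** Six patients per cohort and a 40% benchmark toxicity rate come from Protocol 18.5 and SAP 3.3. The hold and stop rules come from Protocol 9.1 and 14.0. Rates of 10% and 20% are assumed, to give a range. Patients are taken as independent, with the same attributable DLT rate p throughout. DLTs are taken to appear within 2 weeks, and patients 4-6 to be dosed close together.

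**The plan's own figure.** Chance of no DLT in six patients at 40%: (1 - 0.4)^6 = 0.0467. The stated value of under 5% reproduces, and nothing below affects it.

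**The text, followed through cohort 3.** Patient 1 is clean. Patient 2 has a DLT. Patient 3 waits 2 weeks, but for elapsed time and not for a DSMB finding. Whether patient 4 must wait 2 weeks after patient 3 depends on how the closing words about further enrollment in Protocol 9.1 are read. No interval is stated for patients 5 and 6. The only stated stops are a second attributable DLT or a second SAE.

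**How often the hold would miss the first DLT.**

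| Quantity | Formula | 10% | 20% | 40% |
|---|---|---|---|---|
| Any DLT in patients 1-3 | 1 - (1-p)^3 | 0.271 | 0.488 | 0.784 |
| First one in patient 2 or 3 (no hold) | (1-p)[1 - (1-p)^2] | 0.171 | 0.288 | 0.384 |
| Share not held | ratio of the two rows | 63% | 59% | 49% |
| Exactly one in first three, in patient 2 or 3 | 2p(1-p)^2 | 0.162 | 0.256 | 0.288 |

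**What 2-week spacing of patients 4-6 would add if the DSMB clears continuation.** This counts only the cohorts in the last row above. A DLT in patient 4 (probability p) is then the second, and it spares patients 5 and 6. A clean patient 4 followed by a DLT in patient 5 (probability p(1-p)) spares patient 6.

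- Mean spared given that pattern: 2p + p(1-p) = 0.29 / 0.56 / 1.04.
- Mean m per opened cohort: 0.162 x 0.29 = 0.047; 0.256 x 0.56 = 0.143; 0.288 x 1.04 = 0.300.
- Chance g that a cohort has fewer than two DLTs, so that the next may open: (1-p)^6 + 6p(1-p)^5 = 0.886 / 0.655 / 0.233.
- Cohorts 2 and 3 together, given that cohort 2 opens: m(1 + g) = 0.09 / 0.24 / 0.37 patients.
- From trial start, when cohort 1 must also pass at the same rate: g x m(1 + g) = 0.08 / 0.16 / 0.09 patients.

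These are patients not dosed, not DLTs avoided. If the DSMB does not clear continuation, the hold spares everyone still to be dosed.

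**The case against.** **A later DLT is weaker evidence.** One DLT in one patient says more than one in two or three. Under an illustrative uniform prior, the probability that the rate exceeds 40% is:

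- DLT in patient 1: 1 - 0.4^2 = 0.84.
- DLT in patient 2 only: 1 - (3 x 0.4^2 - 2 x 0.4^3) = 0.65.
- DLT in patient 3 only: 0.6^4 + 4 x 0.4 x 0.6^3 = 0.48.

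Pausing when nothing is known at a dose, and otherwise tolerating one DLT in six, is coherent. This stands. A reader might infer that a DLT in patient 2 or 3 deserves a hold because it equals one in patient 1; that does not follow. The case for waiting is narrower: the event counts toward the 2-of-6 stop, and the plan already requires the DSMB to evaluate it.

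**Other brakes exist.** Cohort 2 opens only after six spaced patients, a 4-week wait and DSMB review. The DSMB monitors continuously. Two SAEs trigger a review before enrollment continues, and if SAEs are counted across the trial, a DLT that is also an SAE could be the second. These are real but partial. One DLT does not meet the two-SAE rule alone, a DLT need not be serious, and that rule's scope is not stated.

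**The charter may set a pause.** This stands and limits certainty.

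**Procedure-related events should not be swept in.** The DLT definition covers them, but today's hold does not. The WHO table grades pain needing regular narcotics as 4 and hypertension needing therapy as 3, and both are plausible after craniostomy. A hold on those would be frequent and is not justified here.

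**Conclusion.** The point holds as a gap in the stated rules. A single attributable DLT outside the first patient leads to a DSMB evaluation, but the supplied documents do not tie further dosing to its result. A reader might go further and infer that the plan leaves such a DLT unexamined, that dosing will in fact continue, or that three spaced then three unspaced patients is itself a fault. The documents support none of these: evaluation is required, the charter is unseen, and that pacing is a recognised design.

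The size is modest. The triggering pattern occurs in 0.162 / 0.256 / 0.288 of opened cohorts at assumed rates of 10% / 20% / 40%. The plan expects less: "Based on the animal safety studies, no dose-limiting toxicity is anticipated". Its 40% is a benchmark that also covers procedure-related DLTs. The yield of extra spacing, 0.09 / 0.24 / 0.37 patients once cohort 2 opens or 0.08 / 0.16 / 0.09 from trial start at equal rates, falls further where slow accrual or the two-SAE review already delays dosing. The case rests on safety at little cost, not on large numbers.

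**What to change.** In the Protocol synopsis, Protocol 9.1 and 14.0, and SAP 3.1, state that after any grade 3-4 event assessed as at least possibly related to the SB623 cells, in any patient with others still to be dosed in that cohort, no further patient in the cohort is dosed until the DSMB has evaluated and attributed the event. Leave procedure-only events under the existing DSMB review. If the charter already requires this, a cross-reference is enough.

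Optional, as a sponsor choice: state that patient 4 is dosed no earlier than 2 weeks after patient 3, and return to 2-week spacing for the remaining patients after one DSMB-confirmed attributable DLT.

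Cost: wording, plus DSMB ruling time after such an event. Sample size and visits do not change. The first attributable DLT falls in patients 2-5, where no hold is stated today, in [1 - (1-p)^5] - p = 0.310 / 0.472 / 0.522 of opened cohorts at 10% / 20% / 40%. Holds could be somewhat more frequent, because the trigger precedes the DSMB's attribution. Unrelated laboratory abnormalities would not trigger it. The optional return to spacing adds up to about 4 weeks after exactly one attributable DLT in the first three patients, which occurs in 3p(1-p)^2 = 0.243 / 0.384 / 0.432 of opened cohorts.

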9.2 Duration of Patient Participation

Two years (except if there is an unresolved Grade 2 adverse event at least possibly related to the therapy, in which case the patient will be followed until resolved or reduced to Grade 1).

10.0 STUDY ASSESSMENTS

10.1 Schedule of Study Activities

Table 4 below lists the procedures to be followed throughout the course of the study.

Confidential and Proprietary

	Scr. 1	Scr. 2	Baseline ¹	Enroll ²	Cell Admin	Follow-Up Period						Last Eval.	
Study Day			-2 to-1	-1 to 1	1	2	8						
Study Week	-3	-1	1	1	1	1	2						
Study Month								End of 1 and 2	End of 3 and 4	End of 6	End of 9	End of 12	End of 24
Informed Consent	X ³												
Demographics	Х												
Inclusion/Exclusion	Х		Х										
Medical History	Х	X^4	X ⁵	X^6									
Medication History	Х	X^4	X ⁵	X^6									
Signs & Symptoms	Х	X^4	X ⁵	X^6									
Pregnancy Test ⁷	X ⁸		X										
Physical Exam.	Х		Х									Х	Х
Vital Signs	Х	Х	Х				Х	Х	Х	Х	Х	Х	Х
Chest X-Ray and ECG	Х												
Hematology (Section 15.3)	Х	Х	Х				Х	Х	Х	Х	Х	Х	Х
Serum Chemistry (Sect. 15.3)	Х	Х	Х				Х	Х	Х	Х	Х	Х	Х
INR	Х		Х										
Occult Malig. (Sect. 10.2.2)	Х												
Lipid Panel (Section 15.3)			Х				Х	Х	Х	Х	Х	Х	Х
Cytokines (Section 15.3)			Х				Х	X (mo. 2)	X (mo. 4)	Х	Х	Х	Х
Blood for HLA antibodies	X ⁹												
Head CT					Х								
ImagingHead FDG-PET			Х							Х		Х	Х
ImagingHead MRI	X ¹⁰		Х		X ¹¹	Х	Х	X	Х	Х	Х	Х	Х

Table 4 **Study Procedures Flow Chart**

- ⁶ Only changes since Baseline
- ⁷ Only for women of childbearing potential ⁸ Serum β-HCG at Screening; serum or urine β-HCG at Baseline

¹ Only after documentation of stable stroke by two evaluations within 3 weeks prior to study entry using the NIH Stroke Scale (no more than ± 1 point)

² Enrollment only after all inclusion and exclusion criteria are verified and the patient qualifies for the study

³ Prior to any study-related procedures

⁴ Only changes since Screen 1

⁵ Only changes since Screen 2

⁹ May also be done at a pre-Screen visit

¹⁰ May instead be done at a pre-Screen visit ¹¹ Or CT overlaid with MRI from Baseline

	Scr. 1	Scr. 2	Baseline ¹	Enroll ²	Cell Admin	Follow-Up Period							Last Eval.
Study Day			-2 to-1	-1 to 1	1	2	8						
Study Week	-3	-1	1	1	1	1	2						
Study Month								End of 1	End of 3	End	End	End	End
Study Month								and 2	and 4	of 6	of 9	of 12	of 24
Clinical Stroke Evaluations	X ¹²	X ¹²	Х					X	Х	Х	Х	Х	Х
Cognitive Questionnaire			Х							Х		Х	Х
Blood for antibodies to			Х				X	\mathbf{V} (max 2)	\mathbf{V} (ma \mathbf{A})	Х	Х	X	X
SB623 and for PBMCs			Л				Λ	X (mo. 2)	X (mo. 4)	Λ	Λ	Λ	Λ
Serum Antibod. (see Sect.													
15.6 for assay schedule)													
PBMC Function (see Sect.													
15.7 for assay schedule)													
Adverse Events					Х	Х	Х	X	Х	Х	Х	Х	Х
Concomitant Medications					Х	Х	Х	X	Х	Х	Х	Х	Х

¹² NIHSS and Modified Rankin at Scr. 1 and only NIHSS at Scr. 2

10.2 Pre-study Evaluation and Baseline (Pre-Screen, Scr. 1, Week -3 and Scr. 2, Week -1)

The following will be done prior to performing any study-specific procedures:

• Informed Consent Signed: study-related details will be carefully discussed with the patient. The patient will sign an Informed Consent Form approved by the local Ethics Committee.

10.2.1 Pre-Screen (Optional)

- Blood sample for determination of presence of antibodies to donor SB623 cells with a Luminex value of >1000 MFI (Maximum Fluorescence Intensity): HLA Class I (HLA-A*23:PWMV, HLA-A*68:CGBR; HLA-B*45:FJH, HLA-B*53:KJW; or HLA-Bw4, HLA-Bw6; HLA-Cw*04:SSWB, HLA-Cw*16:01); or Class II (HLA-DRB1 *13:NGUB, HLA-DRB1 *16:02; HLA-DQB1*05:CHZY, HLA-DQB1*05:BK; HLA-DQA1*01:DVB, HLA-DQA1*X, HLA-DRB3,4,5: 3*03:01, HLA-DRB3,4,5: 5*02:02)
- Head MRI

10.2.2 Scr. 1, Week -3

- Inclusion/Exclusion Criteria
- Demographics
- Medical History
- Medication History
- Signs & Symptoms
- Pregnancy Test (serum β-hCG)
- Physical Exam.
- Vital Signs Including Weight
- Chest X-Ray and ECG
- Hematology (Section 15.3)
- Serum Chemistry (Section 15.3)
- INR
- Determination of occult malignancy by occult blood in stools (hemocult test), finding on chest x-ray, carcinoembryonic antigen, prostate-specific antigen (males only), cancer antigen 125 (females only), α-fetoprotein, and β-hCG
- Blood sample for determination of presence of serum antibodies to donor SB623 cells with a Luminex value of >1000 MFI (Maximum Fluorescence Intensity): HLA Class I (HLA-A*23:PWMV, HLA-A*68:CGBR; HLA-B*45:FJH, HLA-B*53:KJW; or HLA-Bw4, HLA-Bw6; HLA-Cw*04:SSWB, HLA-Cw*16:01); or Class II (HLA-DRB1 *13:NGUB, HLA-DRB1 *16:02; HLA-DQB1*05:CHZY, HLA-DQB1*05:BK; HLA-DQA1*01:DVB, HLA-DQA1*X, HLA-DRB3,4,5: 3*03:01, HLA-DRB3,4,5: 5*02:02)
- Imaging (head MRI: only if not done at a pre-screen visit)

• Clinical Stroke Evaluations (NIHSS and Modified Rankin only)

10.2.3 Scr. 2, Week -1 (±2 Days)

The following will be performed:

- Medical History (only changes since Scr. 1)
- Medication History (only changes since Scr. 1)
- Signs & Symptoms (only changes since Scr. 1)
- Vital Signs
- Hematology (Section 15.3)
- Serum Chemistry (Section 15.3)
- Clinical Stroke Evaluations (NIHSS only)

10.3 Baseline and Enrollment (Days -2 to 1, not including weekends)

10.3.1 Baseline (Weekday -1 to -2)

The following will be performed at Baseline:

- Inclusion/Exclusion
- Medical History (only changes since Screen 2)
- Medication History (only changes since Screen 2)
- Signs & Symptoms (only changes since Screen 2)
- Pregnancy Test (serum or urine β-hCG)
- Physical Exam.
- Vital Signs
- Hematology (Section 15.3)
- Serum Chemistry (Section 15.3)
- INR
- Lipid Panel (Section 15.3)
- Cytokines (Section 15.3)
- Imaging (head MRI & FDG-PET)
- Clinical Stroke Evaluations
- Cognitive Questionnaire (Section 23.0, Table 7)
- Blood for antibodies to SB623 and peripheral blood mononuclear cells (PBMC) function assays and for storage of PBMCs (Section 15.7)
- Luminex assay for antibodies to SB623

10.3.2 Enrollment (Days -1 or 1)

Enrollment can only occur after performing all assessments and verifying that the patient meets the inclusion and exclusion criteria for the study.

10.4 Cell Administration (Day 1)

Prior to any procedures, the patient will be queried on the use of any changes in medication since Baseline.

Prior to cell implantation, either a head CT overlaid with the Baseline head MRI or a head MRI alone will be done to determine the exact locations for the implants.

Using the procedures in Section 6.0, surgical and implantation Procedures and Section 10.4, Preparation and Administration, one burr hole will be made in the skull of the patient in a location that will allow ready access to the infarct region. Cells will be implanted using 3 needle tracks with 5 cell deposits for each track at varying depths. Cell implantation will be standardized as to volume ($20 \mu L/deposit$) and rate ($10 \mu L/min$), with spacing between each implant of approximately 5-6 mm.

After cell implantation, the following will be performed:

- Imaging (head CT only)
- Adverse Events
- Concomitant medications

10.5 Follow-Up Period (Study Day 2)

The following will be performed:

- Adverse Events
- Concomitant Medications (see Section 12.0)
- Head MRI (MRI must be read before re-starting any antiplatelet, anticoagulant, or non-steroidal anti-inflammatory agents)

10.6 Follow-Up Period (Study Day 8)

The following will be performed:

- Vital Signs
- Hematology (Section 15.3)
- Serum Chemistry (Section 15.3)
- Lipid Panel (Section 15.3)
- Cytokines (Section 15.3)
- Head MRI
- Blood for antibodies to SB623 and peripheral blood mononuclear cells (PBMC) function assays and for storage of PBMCs (Section 15.7)
- Luminex assay for antibodies to SB623 and PBMC function assay
- Adverse Events
- Concomitant Medications (see Section 12.0)

